**Appendix 7: Combined concept elicitation and cognitive debriefing patient interview guide**

# 1. Interview objectives and overview

## [Note to interviewer]:

The overall objective of this interview is to explore patients' experience of severe, recurrent nasal polyps via the conduct of concept elicitation interviews and to obtain feedback from patients on a series of patient-reported outcome (PRO) instruments designed to assess the symptom and impact experience of nasal polyps via the conduct of cognitive debriefing interviews.

The concept elicitation phase will facilitate the identification of concepts of disease experience that are important to adult patients with nasal polyps and the language they use to talk about the concepts and describe those concepts. The main areas of exploration will be the symptoms experienced by patients. In particular we are interested in the intensity, frequency and duration of each symptom, how bothersome or intrusive each symptom is to each patient, and whether/ how the collective symptom experience of nasal polyps has any impact on the patient's quality of life.

The cognitive debriefing phase will assess a number of PROs including the following:

Sino-Nasal Outcome Test (SNOT-22);

Visual analogue scales (VAS) proposed for use in GSK phase III trial:

Nasal obstruction VAS;

Nasal discharge VAS;

Throat mucus VAS;

Loss of smell VAS;

Facial pain VAS;

Overall VAS symptom score.

The relevance and appropriateness of the each of the items covered by each instrument will be assessed during the cognitive debriefing interview, as will patients' ability to read and consistently understand the item wording, instructions, response options and recall period of each instrument. The cognitive debriefing phase will also investigate how patients define a meaningful change in score, for each item of each instrument.

- **Aim of the concept elicitation phase**

Explore the symptoms experienced by adults with nasal polyps, with particular attention paid to the frequency, intensity, duration of each symptom and how bothersome it is.

Explore the language used by adult nasal polyp patients to describe their disease experience.

Explore how each symptom (individually and collectively) affects the patients' quality of life.

- **Aim of the cognitive debriefing phase**

- Evaluate the relevance of the PRO instruments to nasal polyp patients.

## ADELPHI VALUES

- Evaluate the patients' ability to read and consistently understand the content of the collection of PRO instruments, such as the item wording, instructions, response options and recall period.
- Investigate how patients define a meaningful change in score, for each item of each of the instruments.

*(PRO instruments include: SNOT-22, Nasal obstruction VAS, Nasal discharge VAS, Throat mucus VAS, Loss of smell VAS, Facial pain/pressure VAS and an overall severity of condition VAS scale).*

- **Overview of the interview process**

The interview should be conducted as follows:

1. **Introduction to the study:** Introduce Adelphi Values to the patient. Explain the objectives and the process of the interview.
2. **Consent:** Ensure the patients' written informed consent to participate has been obtained prior to beginning the interview. Also obtain the patients' verbal consent for the interview to be audio-recorded.
3. **Interview:** In the interviews you should ask the patient questions in an open-ended exploratory manner. Lead the patient as little as possible in this part of the interview.

The interview is divided into the following sections:

1. Introduction to the study (5 minutes)
2. Experience of nasal polyps (55 minutes)
3. Cognitive debriefing of the collection of PRO instruments (60 minutes)

In total, the interview should take approximately **120 minutes.**

## 2. Role of the interviewer and instructions

---

### The role of the interviewer before the interview:

1. Check that the patient's clinician has completed the CRF and screener and that the patient meets the inclusion and exclusion criteria.
2. Check the patient has provided written informed consent and provided verbal consent for the interview to be audio-recorded.

### The role of the interviewer during the interview

- **Digital Audio recording.** Ensure that the comments of the patient throughout the interview are clearly recorded on the audio-recording. Audio recordings will be transcribed verbatim. Check the volume settings and positioning of the audio recorder to ensure the clarity of the audio recording prior to the interview making sure recordings are clearly audible. Check that the audio recorder has enough battery power for the duration of the interview. Avoid rustling papers near the recorder or jostling the recorder during the interview as this will lead to inaudible responses.

### The role of the interviewer is to **inquire** and **support**:

Do not give your own point of view

Be patient and accept silence during open-ended questioning to make sure the patient has time to think about her/his response

Help the patient stick to the topics intended in the guide (but not necessarily in the order presented in the guide)

Help the patient avoid repeating himself or herself

Help the patient cross-reference and make connections that they would not do spontaneously

Ask the patient to clarify any comments that you are not certain you understood and for the benefit of the recording

Ask the patient to explain any vague reference or comment that is pertinent to the research question

**Most importantly:** avoid biasing or leading the patient

**As much as possible your questions should be open-ended and general rather than specific – use suggested probes to follow-up on topics of interest if not adequately discussed in response to the open questions.**

**It is very important that you do not lead the patient with your questions or remarks.** Ask all questions in as open-ended a manner as possible; take care not to bias the patient's response one way or the other. Below for most questions, we have provided a number of possible probes that should help the patient explain his or her thinking when s/he is talking about the topics of interest. These probes are

ADELPHI VALUES

**optional** and do not have to be asked if, when asked the initial question, the patient provides a fully elaborated response and addresses the topics noted in the probes. The probes are only provided for use when the patient finds it difficult to answer your questions, if s/he is reluctant to speak at length about experiences or if key topics of interest have not been elicited spontaneously. You may have to invent your own probes or reword the probes indicated in the interview guide; this is fine. As a fully trained and experienced interviewer we rely on your judgment as to when more information is required from the patient and for you to probe as appropriate.

POSSIBLE NON-LEADING PROBES MIGHT INCLUDE:

- Can you describe exactly how that feels?
- Tell me more about that.
- How does that affect you?
- Can you talk more about \_\_\_\_\_?
- How often does that happen?
- How long does that last?
- Is there anything that makes it better or worse?

During the interview, it is not essential for you to ask the questions in exactly the way that they are written in this guide and for some interviewees it may be necessary for you to reword questions as a means to enable open-discussion. If you reword a question; however, you should be sure to avoid biasing the patient’s response. If a topic has been covered sufficiently in an earlier part of the discussion it is not necessary to go over it again later if this topic comes up later in the interview guide.

If the patient directs any questions to you that are of a medical nature, please explain that you are not a medical professional and that the patient should direct any medical queries to his or her doctor or nurse.

**Using the interview guide**

Throughout this guide we have coded the questions and instructions so that it is clear which questions are required and which are probes and do not necessarily need to be asked. The code is as follows:

Blue font	These are instructions to you
	These are statements that you are to read aloud word-for-word
1.	Questions prefixed by a specific number must be posed to all patients
•	All probes are bulleted – these do not need to be used specifically but are included to assist you in drawing further information from the patients

**Adverse event reporting**

If the respondent mentions an adverse event experienced while taking a product made by the sponsor company, or a product you suspect is a product made by the sponsor company, whether it is considered serious (see definitions below) or not, you should make a note of it and at the end of the interview go through the ‘**Adverse Event Form**’. At this time please state the following to the patient:

🗣️ *“During the interview you mentioned a problem that you experienced while taking [product name]. The sponsor of this research needs to collect information about their products in order to continue making them as safe and effective as possible. Every report they receive contains potentially useful information. I would like to spend a couple of minutes with you now to collect some more details. Is that OK with you?”*

**If yes** *“Thank you. The information you provide will be sent to the study sponsor, who may wish to contact your doctor for further information. If you agree to provide your doctor’s name, this will not be linked in any way to your other responses given during the interview. Are you happy to provide the name of your doctor?”*

(If the respondent subsequently says no, then go to the ‘If no’ section)

**If no** *“OK that’s fine. However, as the information you were given about this study explained, we do have to report this problem to the sponsor. This will be done anonymously, and none of your personal details will be shared with them.”*

You should complete the **‘Adverse Event Form’** with as much detail as you can retrieve.

Remember, an Adverse Event must be reported when the following are present:

**PREP – Patient, Reporter, Event, Product**

**1. A Patient or group of patients**

- Identifiers such as age, age group, birth date, gender, role, profession should be collected if available, if not the event should still be reported.

**2. An identifiable Reporting source**

- Information that identifies the reporter, establishing knowledge of the reportable event in an identifiable consumer.
- A reporter can be a patient, doctor, patient’s parent, friend, colleague or caregiver.

**3. An adverse Event**

- Description of at least one event or product complaint.

**4. A suspect Product**

- This must be one of the products being marketed by the company that we are doing research for.

**Remember:** The event need not have a causal relationship with the treatment or usage.

An adverse event is:

***“Any untoward medical occurrence in a patient administered a sponsor medicinal product and which does not necessarily have to have a causal relationship with this treatment. An adverse event can be any unfavorable and unintended sign (e.g. an abnormal laboratory finding), symptom, or disease temporally associated with the use of a medicinal product, whether or not considered related to the medicinal product.”***

## ADELPHI VALUES

An adverse event can also be revealed through follow up on a product complaint (PC). For these purposes a PC is a complaint specific to the product itself, or packaging, as opposed to its effect on the patient. Examples include damaged or missing tablets; wrong strength or color of tablets; damaged packaging; a label that cannot be read; a liquid that should be clear but is cloudy or contains unexpected particles; a bent needle, a broken syringe; a missing patient information leaflet or the identification of a potentially counterfeit medicine.

Cases where a woman is pregnant or breastfeeding while taking a company's medicine also need to be collected even if no AE is specifically cited. In these instances, it is important to capture whether or not there were any complications during the pregnancy or any congenital abnormalities occurring in the baby.

A **serious adverse event** (which should be reported to the FDA) is any undesirable experience associated with the use of a medical product in a patient when the patient outcome is:

### **Death**

Report if you suspect that the death was an outcome of the adverse event, and include the date if known.

### **Life-threatening**

Report if suspected that the patient was at substantial risk of dying at the time of the adverse event, or use or continued use of the device or other medical product might have resulted in the death of the patient.

### **Hospitalization (initial or prolonged)**

Report if admission to the hospital or prolongation of hospitalization was a result of the adverse event. Emergency room visits that do not result in admission to the hospital should be evaluated for one of the other serious outcomes (E.g., life-threatening; required intervention to prevent permanent impairment or damage; other serious medically important event).

### **Disability or permanent damage**

Report if the adverse event resulted in a substantial disruption of a person's ability to conduct normal life functions, i.e., the adverse event resulted in a significant, persistent or permanent change, impairment, damage or disruption in the patient's body function/structure, physical activities and/or quality of life.

### **Congenital anomaly/birth defect**

Report if you suspect that exposure to a medical product prior to conception or during pregnancy may have resulted in an adverse outcome in the child.

### **Required intervention to prevent permanent impairment or damage (devices)**

Report if you believe that medical or surgical intervention was necessary to preclude permanent impairment of a body function, or prevent permanent damage to a body structure, either situation suspected to be due to the use of a medical product.

### **Other serious (important medical events)**

Report when the event does not fit the other outcomes, but the event may jeopardize the patient and may require medical or surgical intervention (treatment) to prevent one of the other outcomes.

Date:   /   / 2017  
MM DD

Center Number: /\_\_\_/\_\_\_/

Participant N°: /\_\_\_/\_\_\_/

## ADELPHI VALUES

Examples include allergic bronchospasm (a serious problem with breathing) requiring treatment in an emergency room, serious blood dyscrasias (blood disorders) or seizures/convulsions that do not result in hospitalization. The development of drug dependence or drug abuse would also be examples of important medical events.

### 3. Interview introduction (5 minutes)

---

This interview should last approximately **120 minutes**.

#### **INTRODUCE YOURSELF AS WORKING FOR ADELPHI VALUES**

- 🗣️ *“My name is \_\_\_\_\_ and I work for a company called Adelphi Values. Adelphi Values is a research company which works with pharmaceutical companies to develop questionnaires for use in clinical studies to assess the impact of health conditions on people’s lives. GlaxoSmithKline, the sponsor of this study, would like to explore individuals’ experience of nasal polyps to find out more about the symptoms experienced and how the condition affects their lives.”*

#### **EXPLAIN THE AIM AND PROCESS OF THE INTERVIEW TO THE PATIENT**

- 🗣️ *“We would like to talk to you about your experience of living with nasal polyps, particularly the symptoms you experience and how having nasal polyps may impact you. This part of the interview will take approximately 55-minutes.”*
- 🗣️ *“We would also like to obtain your opinion of a number of questionnaires, including their relevance to nasal polyps and your understanding of their content. This part of the interview will take approximately 60-minutes.”*
- 🗣️ *When we’re finished with the interview, you will receive a payment of \$200 to thank you for your time and your participation in the interview.”*

#### **REASSURE THE PATIENT OF CONFIDENTIALITY**

- 🗣️ *“Your name and contact information will remain with Adelphi Values and will only be accessible to researchers directly involved with this project. Any information you provide will be reported in a way that protects your privacy by avoiding any mention of your name or other information that could identify you.*

#### **AUDIO-RECORDING THE INTERVIEW**

- 🗣️ *“The interview today will be audio-recorded to enable us to pay careful attention to what you say and to make certain we accurately capture the information that you provide to us during the interview. After the interview the audio-recording will be transcribed (written out).”*
- 🗣️ *“An anonymized recording or written version of the interview may be shared with the study sponsor. This means that we will take any information out of the interview that might identify you, like names or places, and any data that you provide will be assigned an ID number.”*
- 🗣️ *“Please try to speak relatively loudly so that your comments can be heard and are clear on the recordings.”*
- 🗣️ *“Please be honest in your responses and don’t be afraid to voice any opinions. We want to know about your experience and opinions, not those of your doctor or anyone else.”*
- 🗣️ *“If you do not understand a question, please ask for the question to be repeated and explained.”*

ADELPHI VALUES

💡 **IMPORTANT:** *“If you find any of the questions difficult to answer, please let me know. You do not have to answer any questions you do not want to. You may leave the interview at any point and you may decline to answer any question.”*

**At this point, turn on the audio-recorder and ask the patient the following questions:**

- 💡 *“Do you agree to participate in this interview?”*
- 💡 *“Do you agree to have this interview audio-recorded?”*
- 💡 *“Do you have any questions at this point?”*

## 4. Concept elicitation: exploration of the patient experience of nasal polyps (55 minutes)

---

- Nasal polyp symptoms (35 minutes)**

🗣️ *“This is the first section of the interview where I will ask you general questions about your experience of having nasal polyps.”*

**[Note to the interviewer]:** First ask the participant how they refer to their condition and use this terminology in place of ‘nasal polyps’ throughout the interview.

**5. When you talk to your family or friends about your nasal condition, how do you refer to it? What do you call it? Is it ok to use this term throughout the interview?**

**[Interviewer]:** Enter term/s used \_\_\_\_\_

🗣️ *“We are now going to talk about the symptoms that you experience as a result of your nasal polyps.”*

**6. Tell me about your experience of nasal polyps.**

**7. Tell me about the symptoms that you experience related to your nasal polyps.**

**[Note to the interviewer]:** List down every symptom that the patient mentions spontaneously as a symptom that they experience. You can use the ‘symptom table’ below to record symptoms that the patient mentions spontaneously. If the symptom is not on the list, please write it down.

### SYMPTOM LIST

Symptom	Tick if mentioned spontaneously (✓)
Congestion	
Runny nose	
Nasal swelling	
Loss of smell	
Change in smell	
Nose bleed	
Post-nasal drip/throat mucus	
Nasal pain	
Nasal pressure	
Sneezing	
Visible polyps	

Symptom	Tick if mentioned spontaneously (✓)
Mucus/catarrh	
Nasal tightness	
Sinus blockage	
Sinus inflammation	
Sinus infections	
Difficult breathing	
Wheezing	
Cough	
Head/facial pressure	
Headache	
Dizziness	
Dry throat/mouth	
Loss of taste	
Distorted voice	
Ear congestion	
Illness and infection	
Patient mentioned symptoms not currently in list:	

**[Note to interviewer]:** Now ask the participant the following questions about each sign/symptom that they mentioned spontaneously. Allow the participant to answer spontaneously at first and only probe further if the participant is having difficulty discussing his/her experience or hasn't previously mentioned the probed topics. Please note that the probes are to be used as a guide and they may not all need to be asked.

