### **2.2 Secondary**

#### **Combined concept elicitation (CE) and cognitive debriefing (CD) interviews:**

To identify through open-ended questioning the concepts that are important to patients with severe, recurrent, nasal polyps, who have been treated with surgery and the language they use to describe their disease experience. The main areas of exploration will be the symptoms with particular attention paid to the frequency, severity, duration and bother of each symptom, patients' surgical decision-making and surgical/treatment experience and the functional and HRQoL impact experienced by patients.

To cognitively test and explore the content and face validity of existing PRO instruments (single item VAS and SNOT-22) via assessment of the relevance and appropriateness of the items included in the instruments and the participants' ability to read, and consistently understand the instrument item wording, instructions, response option and recall period. The CD interviews will:

- Explore participants' ability to read and consistently understand the item wording, instructions, response options and recall period of the overall and single item VAS and SNOT-22.
- Explore the relevance and appropriateness of all of the items covered by the instruments based on the symptom experience of patients with nasal polyps.
- Verify if the key concepts identified in the concept elicitation phase of the study are adequately assessed by the PRO instruments (confirmation of face validity) and if any gaps exist, provide recommendations for how these could be addressed.
- Explore what level of change in symptoms and/or impacts the patients might consider meaningful. (E.g. what level of change they might consider noticeable and important in response to treatment, and how changes on the item scores might relate to changes in their experience in their symptoms and/or functional impacts.

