**[Note to interviewer]: For each symptom mentioned ask the following questions:**

Symptom description	
 
• How would you describe this symptom? How does it make you feel?
 
• Tell me about any additional words you use to describe this symptom, if at all.
 

Frequency	
 
• How often do you experience this symptom?
 
• Does the frequency vary/has it changed over time? Please tell me about this.
 
• Does the frequency vary in the daytime versus the nighttime? Tell me about that.
 
• Is it a constant symptom or does it come and go? Tell me about that.
 

Severity	
 
• How would you describe the severity of this symptom?
 
• Does the severity vary/has it changed over time? Please tell me about this?
 
• Does the severity change in the daytime versus the nighttime? Time me about that
 
• How would you describe mild, moderate and severe [insert symptom]?
 

Duration	
 
• How long does this symptom typically last for?
 
• Does the duration vary/has it changed over time? Please tell me about this.
 

Impacts	
 
• How does this symptom affect you in your daily life?
 
• How bothersome is this symptom for you? Please tell me more about that. 
 
○ Physically?
 
○ Doing your daily/usual activities?
 
○ In doing things/relationships with family or friends?
 
○ Emotionally?
 
○ At school/work?
 
 
 

Worsening / Improvement	
 
• Tell me about anything that makes this symptom worse.
 
• Tell me about anything that makes this symptom better.
 

Relation to other symptoms	
 
• Do you experience this symptom on its own or at the same time as other symptoms? Please tell me more about that.
 

**[TO INTERVIEWER]** Please probe on those symptoms in the ‘symptom list’ above, that were not spontaneously mentioned by the participant. Please assess relevance of the symptom first. If the participant experiences the symptom in question please ask the additional questions detailed in the table above.

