**8. Have you ever experienced any of the following symptoms as part of your nasal polyps?**

**9. Are there any other symptoms of nasal polyps not already discussed that you have experienced? Please tell me about them.**

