
What does “mucus in the throat” mean to you?            Would you use any other words to describe this term?
	
Do you experience this as part of your nasal polyps?            Please mark your answer on the line.            What number from 0-100 does this line represent?            Does your experience of mucus in throat change in severity over 24 hours?
	
What time frame were you thinking about when answering this question?            Was it easy or difficult to remember over the past 2 weeks?
	
How easy or difficult was it for you answer this question? Why?            What change in score would make a difference to you and why?

[LOSS OF SMELL VAS] 'Please rate your loss of smell at its worst over the previous 24 hours'  [SCALE] 0 (none) – 100 (as bad as you can imagine)
			

What does “loss of smell” mean to you?
	
Do you experience this as part of your nasal polyps?            Please mark your answer on the line.            What number from 0-100 does this line represent?            Does your experience of loss of smell change in severity over 24 hours?
		
How easy or difficult was it for you answer this question? Why?            What change in score would make a difference to you and why?

[FACIAL PAIN VAS] 'Please rate your facial pain or pressure at its worst over the previous 24 hours'  [SCALE] 0 (none) – 100 (as bad as you can imagine)
			
	
Do you experience this as part of your nasal polyps?            Please mark your answer on the line.            What number from 0-100 does this line represent?
		
How easy or difficult was it for you answer this question? Why?            What change in score would make a difference to you and why?

Date:  /  / 2017  
MM DD

Center Number: /\_\_\_/\_\_\_/

Participant N°: /\_\_\_/\_\_\_/

ADELPHI VALUES

Understanding	Relevance	Recall period	Response Options

[OVERALL VAS SYMPTOM SCORE] ‘Overall, please rate your nasal polyps symptoms at their worst over the previous 24 hours’
 
[SCALE] 0 (none) – 100 (as bad as you can imagine)
			

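### The concept-elicitation symptom list prompts for facial pressure but not facial pain, so half of one proposed Phase III VAS is elicited less evenly than the other VAS concepts

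*Combined protocol and SAP*

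**What the plan says.** In the interview guide (Appendix 7, concept elicitation, or CE), the interviewer first asks open questions and ticks each symptom that is volunteered on a printed list. For anything else the instruction is: "If the symptom is not on the list, please write it down". The interviewer then turns to the listed symptoms "that were not spontaneously mentioned by the participant. Please assess relevance of the symptom first", and follows up those the participant has. Question 8 carries this prompt: "Have you ever experienced any of the following symptoms as part of your nasal polyps". The note on using the guide makes it compulsory: "Questions prefixed by a specific number must be posed to all patients".

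The only facial row on the list is "Head/facial pressure". The corresponding scale proposed for Phase III reads: "Please rate your facial pain or pressure at its worst over the previous 24 hours". The guide calls this scale the Facial pain VAS when it lists the instruments. SNOT-22 item 11 also joins pain and pressure, and item 10 is ear pain.

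Section 2.2 makes frequency, severity, duration and bother of each symptom the main CE topics. It also sets an aim for cognitive debriefing (CD): "Verify if the key concepts identified in the concept elicitation phase of the study are adequately assessed by the PRO instruments". Section 4 (Analysis of interviews) allows the number of participants mentioning an issue to be reported, but rules out quantitative analysis of those numbers.

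**The concern.** The list determines which symptoms are raised with everyone in CE. If the concept behind one proposed scale is missing from it while the concepts behind the others are present, the scales are being compared on data gathered in different ways. A thin CE account of facial pain could then reflect the guide rather than the patients. That matters for a scale that joins pain and pressure, because the protocol elsewhere treats the two as separable: the case report form (Appendix 4, question 3 on nasal polyps) has a box for each, and the debrief of SNOT-22 item 11 asks whether they differ.

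**Working it through.** No formula in the plan bears on this; the check sets the passages side by side.

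**1. Count the list.** The two parts of the Appendix 7 symptom list have 11 + 16 = 27 printed rows. None is facial pain or ear pain.

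**2. Match it to the five single-symptom VAS.**

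| VAS concept | Row on the CE list |
|---|---|
| Nasal obstruction | Congestion; Sinus blockage (by synonym; the case report form groups blockage, obstruction and congestion) |
| Nasal discharge | Runny nose; Mucus/catarrh (by synonym) |
| Throat mucus | Post-nasal drip/throat mucus |
| Loss of smell | Loss of smell |
| Facial pain or pressure | Head/facial pressure only; no row for pain |

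So 4 of 5 are fully represented. Nasal pain and Headache are the nearest rows to facial pain, but they name other sites. For ear pain the nearest row is Ear congestion.

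**3. Who is prompted.** Question 8 is numbered, so the listed symptoms not already volunteered are to be raised in all 20 + 10 = 30 planned interviews.

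**4. Routes for an unlisted symptom in CE.** There are three: spontaneous mention with a write-in; the open Questions 9 and 26, which are also compulsory but still depend on the participant thinking of the symptom; and a probe of the interviewer's own, which the guide permits but does not require.

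**5. What CD adds for facial pain.**

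| Topic | CE follow-up for a symptom the participant has | CD, SNOT-22 item 11 |
|---|---|---|
| Severity and frequency | Yes | Yes, separately for pain and for pressure |
| Pain and pressure the same or different | No set question | Yes |
| Duration | Yes | No |
| Bother and daily impact | Yes | No |
| What makes it better or worse | Yes | No |

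The Facial pain VAS debrief asks about experience of the joined concept, the rating, ease of answering and meaningful change. It does not fill the last three rows.

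**6. Direction and size.** Questions 10 to 12 ask for the worst, most frequent and most bothersome of the symptoms the participant has described, so a symptom that never came up cannot be chosen. If a share v of those with facial pain mention it without a listed prompt, CE records v of the true number, a shortfall of 1 − v. For a symptom that is prompted in every interview the shortfall is close to zero. The documents give neither v nor how common facial pain is, so the direction follows but no figure does.

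**The case against.** The strongest reply is that CD already does much of the work. Every participant completes SNOT-22 item 11. The guide then has the interviewer ask what facial pain and facial pressure each mean, whether they differ, where on the face they are felt, whether one question suits both, and what separate scores would be. This stands for severity, frequency and the pain-versus-pressure question, although the guide also says that not every debriefing probe has to be used. It does not stand for duration, bother, daily impact or aggravating and relieving factors. CD answers are also prompted by the instrument under test.

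Second, the contrast with listed symptoms is softer than it looks. The CE follow-up questions are bulleted, and the guide makes bulleted probes optional, so a listed symptom is sure of being raised but not of being fully explored. This stands. The difference lies in the prompt, and the follow-up only becomes more likely through it.

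Third, Question 9 comes straight after prompts on head/facial pressure, headache and nasal pain, which may cue facial pain, and a participant's worst symptom is the one most likely to be volunteered. Both points are plausible and would shrink the effect; neither makes ascertainment equal.

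Fourth, prompting might contaminate elicitation. This does not stand: prompts follow the open questions, and the tick column already separates spontaneous mentions.

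**Conclusion.** The gap is real but modest. In CE, four of the five single-symptom VAS concepts are prompted in every interview; for the fifth, only pressure is. CE descriptions of facial pain, any mention counts that are reported, and its place in Questions 10 to 12 may be understated relative to the other VAS concepts. This assumes that interviewers follow the guide as written and that some participants with facial pain would not raise it unprompted. The size cannot be derived from the documents.

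A reader might infer three stronger things, none of which the documents support:

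- **That facial pain is recorded in the study only when volunteered.** This fails because CD raises it with everyone, the physician can tick it on the case report form, and CE has the open questions and optional probes.
- **That the omission could hide a gap in instrument coverage.** The check in Section 2.2 runs from CE concepts to the instruments, and facial pain is already in both. Under-eliciting it cannot conceal that it is missing from them.
- **That the bias can be put at some percentage.** Any such figure would rest on assumed prevalence and volunteering rates, and Section 4 plans no quantitative analysis of mentions.

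This is a cheap improvement to the guide, not a threat to the study.

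**What to change.** In the Appendix 7 symptom list, split the row Head/facial pressure into *Facial pain* and *Head/facial pressure*, and add *Ear pain*. Keep the spontaneous-mention tick for the new rows so that prompted and unprompted reports stay separate in the analysis. The list goes from 27 to 27 + 1 + 1 = 29 rows, and the VAS whose named concepts are all prompted go from 4 of 5 to 5 of 5.

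The cost is interview time. If the 35-minute symptom section were spread evenly over the present rows, each would take 35/27 ≈ 1.3 minutes, so two more would take about 2.6 minutes; this is less for participants without these symptoms. No sample-size or analysis text changes.

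The change does not turn the list into a mirror of the SNOT-22, and need not. Need to blow nose and Fatigue would still have no row, and Thick nasal discharge would still match only loosely. The aim is even prompting across the proposed VAS concepts, with ear pain added because it is a SNOT-22 item at the same small cost.
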